# **LIST OF ABBREVIATIONS**

ACIP	Advisory Committee on Immunization Practices
AE	Adverse Event/Adverse Experience
CFR	Code of Federal Regulations
CGHATS	Center for Global Health and Translational Science
CRU	Clinical Research Unit
DHHS	Department of Health and Human Services
eCRF	Electronic Case Report Form
EDC	Electronic data collection
FDA	Food and Drug Administration
FWA	Federalwide Assurance
GCP	Good Clinical Practice
GMT	Geometric Mean Titer
HDCV	Human diploid cell vaccine
HIV	Human Immunodeficiency virus
HRIG	Human Rabies Immunoglobulin
HRPO	Human Research Protection Office
ICF	Informed Consent Form
ICH	International Conference on Harmonisation
ID	Intradermal
IM	Intramuscular
IRB	Institutional Review Board
mL	milliliter
NIH	National Institute of Health
OHRP	Office for Human Research Protections
PBMC	Peripheral Blood Mononuclear Cell
PCECV	Purified chick embryo cell vaccine
PEP	Post exposure prophylaxis
РО	per os (oral)
PP	Per protocol
PI	Principal Investigator
QA	Quality Assurance
QAIP	Quality Assessment and Improvement Programs

· .

QC	Quality Control
RFFIT	Rapid fluorescent foci inhibition test
RVNA	Rabies virus neutralization assay
SAE	Serious Adverse Event/Serious Adverse Experience
SOP	Standard Operating Procedure
SSP	Study Specific Procedure
SUNY	State University of New York
UMU	Upstate Medical University
US	United States
USAMRMC	United States Army Medical Research and Materiel Command
WFI	Water For Injection
WHO	World Health Organization

\*

planned	particip	ation dur	ing the p	resent tr	ial period	d, in anot	ther
		stigating	a vaccin	e, drug,	medical o	device, o	r medical
•							
	•		•				
	-		-		-		
5. Any major psychiatric disorder, such as severe depression, severe							
_				•			
			-	-		or anxiety	/ alsoraer
						the etue	ly or 20
	•			•			ly or 30
	•	•					ed an
		_	, and the	ii use Wi	ii iiot be	ooi isidei	ou an
			disorder	such a	s HIV infe	ection co	ommon
_	-	-					
			•			эалогар	J ·
•			•	. •	•	e site inv	estigator.
	Group 1 Group 2 Group 3 Group 4 Subjects mutrial enrollm 1. Provide 2. Willing to duration 3. Male or 4. In good A subject fut enrollment: 1. Subject conside menopal effective weeks plast vace 2. Participal planned clinical to procedure that are 4. Previous 5. Any majanxiety of disorder that are 6. Use of a days presimmuno exclusion 7. Any immuno variable 8. History of	Day   0   Group 1   Group 2   Group 3   Group 4   IM   Subjects must meet trial enrollment: 1. Provide signed a 2. Willing to comply duration of the s 3. Male or female, 4. In good general   A subject fulfilling at enrollment: 1. Subject is pregn considered of no menopausal for effective method weeks prior to the last vaccination. 2. Participation in the planned participic clinical trial investored procedure.   3. Previous history 4. Previous history 4. Previous history 5. Any major psychanxiety disorder disorders, or seinthat are well con 6. Use of any immunosupprese exclusion criteria 7. Any immunosupprese exclusion criteria 7. Any immunosupprese exclusion criteria 8. History of renal in the plant of the pl	Day       0       3         Group 1       Group 2       Group 3         Group 4       IM       IM         Subjects must meet all of the trial enrollment:       1. Provide signed and dated and duration of the study         3. Male or female, aged ≥ 1       4. In good general health based and duration of the study         3. Male or female, aged ≥ 1       4. In good general health based and duration of the enrollment:         1. Subject fulfilling any of the enrollment:       1. Subject is pregnant, or last considered of non-childbout menopausal for at least and effective method of controlled and the enrollment weeks prior to the first variant vaccination.         2. Participation in the 4 weeks planned participation duration clinical trial investigating procedure.       3. Previous history of received anxiety disorder, psychological disorders, or seizures. History disorder, psychological disorders, or seizures. History disorder, psychological immunosuppressive druggexclusion criteria.         6. Use of any immunosuppressive druggexclusion criteria.       7. Any immunosuppressive druggexclusion criteria.         7. Any immunosuppressive drugges immunodeficiences.       8. History of renal insufficiences.	Group 1 Group 2 Group 3 Group 4 IM IM IM Subjects must meet all of the following trial enrollment:  1. Provide signed and dated informed 2. Willing to comply with all study produration of the study  3. Male or female, aged ≥ 18 to ≤ 60 4. In good general health based on a subject fulfilling any of the following enrollment:  1. Subject is pregnant, or lactating, or considered of non-childbearing promenopausal for at least 1 year, sureffective method of contraception weeks prior to the first vaccination last vaccination.  2. Participation in the 4 weeks preceplanned participation during the procedure.  3. Previous history of receiving the result of the first vaccination in the second procedure.  4. Previous history of receiving the result of the first vaccination during the procedure.  5. Any major psychiatric disorder, suranxiety disorder, psychosis, schizdisorders, or seizures. History of that are well controlled are not extend that are well controlled are not extend days previously. Topical steroids immunosuppressive drug and the exclusion criteria.  7. Any immunosuppressive disorder variable immunodeficiency, actives thistory of renal insufficiency or results.	Day       0       3       7       14         Group 1       IM       IM       IM         Group 3       IM       IM       IM         Group 4       IM       IM       IM       IM         Subjects must meet all of the following criteria trial enrollment:         1. Provide signed and dated informed conse duration of the study       3. Male or female, aged ≥ 18 to ≤ 60 years of the study         3. Male or female, aged ≥ 18 to ≤ 60 years of the study       4. In good general health based on medical strial enrollment:         1. Subject fulfilling any of the following criterial enrollment:       1. Subject is pregnant, or lactating, or of child considered of non-childbearing potential, and menopausal for at least 1 year, surgically effective method of contraception or abstitute weeks prior to the first vaccination and unlast vaccination.         2. Participation in the 4 weeks preceding the planned participation during the present the clinical trial investigating a vaccine, drug, procedure.         3. Previous history of receiving the rabies value.         4. Previous history of receiving the rabies wanciety disorder, such as seanxiety disorder, psychosis, schizophrenia disorders, or seizures. History of mild depthat are well controlled are not exclusion of the succina such as seanxiety disorder, such as variable immunodef	Day         0         3         7         14         17           Group 1         IM         IM         IM           Group 2         IM         IM         IM           Group 3         IM         IM         IM           Group 4         IM         IM         IM         IM           Subjects must meet all of the following criteria in order trial enrollment:         1. Provide signed and dated informed consent form           2. Willing to comply with all study procedures and be duration of the study           3. Male or female, aged ≥ 18 to ≤ 60 years on day of           4. In good general health based on medical history a           A subject fulfilling any of the following criteria will be exempted and the study           3. Male or female, aged ≥ 18 to ≤ 60 years on day of           4. In good general health based on medical history a           5. Subject is pregnant, or lactating, or of childbearing considered of non-childbearing potential, a female menopausal for at least 1 year, surgically sterile, or effective method of contraception or abstinence from weeks prior to the first vaccination and until at least last vaccination.           2. Participation in the 4 weeks preceding the first trial planned participation during the present trial period clinical trial investigating a vaccine, drug, medical or procedure.           3. Previous history of receiving the rabies vaccine.         4. Previous history of receiving rabies immune globul for the previous h	Day         0         3         7         14         17         21           Group 1         IM         IM         IM         IM           Group 2         IM         IM         IM         IM           Group 3         IM         IM         IM         IM           Group 4         IM         IM         IM         IM           Subjects must meet all of the following criteria in order to be el trial enrollment:         1. Provide signed and dated informed consent form           2. Willing to comply with all study procedures and be available duration of the study         3. Male or female, aged ≥ 18 to ≤ 60 years on day of inclusion           4. In good general health based on medical history and physical procedure.         4. In good general health based on medical history and physical enrollment:           1. Subject fulfilling any of the following criteria will be excluded to enrollment:         4. In good general health based on medical history and physical enrollment:           1. Subject fulfilling any of the following criteria will be excluded to enrollment:         4. In good general health based on medical history and physical enrollment:           1. Subject fulfilling any of the following criteria will be excluded to enrollment:         6. Use of non-childbearing potential, a female must be menopausal for at least 1 year, surgically sterile, or using a effective method of contraception or abstinence from at least 1 year, surgically sterile, or using a effective method of contracep

place the subject at an unacceptable risk of injury or render the subject unable to meet the requirements of the protocol. 10. Previous adverse reaction to any of the antimalarial drugs used in this study. Temporary Exclusion Criteria: Moderate or severe acute illness/infection (according to investigator judgment) or febrile illness (temperature ≥ 38.0°C [≥ 100.4°F) on the day 0. A prospective subject should not be included in the study until the condition has resolved or the febrile event has subsided. If the delay for the febrile illness exceeds the window between screening and Day 0, or if deemed necessary by the investigator, a prospective subject may be re-screened once the fever has resolved. Recent or scheduled receipt of any vaccine 4 weeks prior to day 0. Randomization: Randomization will be performed through a computer generated process. A standard permuted-block design will be used for randomization/allocation in order to avoid undesirable differences in the numbers of patients assigned to each group. The randomization schedule will be generated by our statistician using SAS 9.3 PROC PLAN. Variable block sizes will be kept confidential from the protocol to reduce the predictability of the treatment assignments. Subjects who withdraw prior to first vaccination will be replaced. Licensed RabAvert® rabies vaccine (Novartis): 1.0 mL reconstituted freeze dried Product. vaccine containing ≥ 2.5 international units of rabies antigen Formulation, administered intramuscularly (IM). Dose. Route of Administration Chloroquine: Chloroquine phosphate two 250 mg tablets containing 150 mg base administered weekly, orally. Malarone: 250 mg Malarone tablet containing 250 mg atovaquone and 100 mg proquanil hydrochloride administered daily, orally. Doxycycline: 100 mg tablet administered daily, orally. **Objectives: Primary:** Compare GMT at 14 days post completion of four dose PEP with PCECV in each of the malaria prophylaxis groups with control to determine if a fifth dose of PEP at that point would be of any added value. **Secondary:** To evaluate GMT over protective titer prior to third dose, fourth dose and 28 days post fourth dose of PCECV. **Exploratory:** Cell Mediated Immunity, Proteomics if differences in the immune responses are seen, Urine analysis in chloroquine group. Primary: GMT by RFFIT at 14 days post completion of four doses PEP **Endpoints:** 

50 mey 2010

	in prophylaxis groups vs. control group
	Secondary: GMT by RFFIT prior to third or fourth dose of rabies
	vaccine and 28 days post fourth vaccine in prophylaxis groups vs control
	group.
	Exploratory: Cell Mediated Immunity, Proteomics if differences in the
	immune response are seen, Urine analysis in chloroquine group.
Statistical	This will be a descriptive study to assess immunogenicity of a licensed
Methods:	rabies vaccine using recommended dosage schedules in the presence
	of malaria chemoprophylaxis. No formal statistical hypothesis tests will
	be conducted. Descriptive analyses will be based on the per-protocol
	analysis sets.
	Exploratory statistical analyses of final data may be conducted, if
	indicated by the descriptive results. Parametric, non-parametric and
	resampling (bootstrapping) methods for statistical inference may be
	used in exploratory analyses, based on data compliance with
	assumptions of methods. P -values ≤ 0.05 will be considered significant
	and p-values ≤ 0.10 will be considered a trend. Confidence intervals will
	be constructed at $\alpha$ =0.05 and $\alpha$ =0.10. When necessary, p-value
	corrections for multiple comparisons will be applied.
	Descriptive and any inferential analyses will be carried out using SAS
	Version 9.2 (or higher), which is licensed and supplied by SAS Institute,
	Cary, NC, USA.
	-

· .

#### 2 INTRODUCTION: BACKGROUND INFORMATION AND SCIENTIFIC RATIONALE

#### 2.1 Background Information

Rabies is present on all continents and enzootic in most African and Asian countries where U.S. military personnel deploy, including countries where malaria is also endemic and where U.S. military personnel are required to take malaria prophylaxis. (1). The incubation period for rabies can be as long as 10 years following infection, placing soldiers who have been exposed, but not rabies vaccinated, at risk for a prolonged period of time. Current DOD policy does not require routine vaccination prior to deployment in rabies enzootic countries. The death of a U.S. soldier in 2011 prompted a survey of other soldiers deployed at the same time. It was determined that 140 out of 8,600 screened had exposures for which post-exposure prophylaxis was indicated but did not seek medical attention (2).

Antimalarial drugs, chloroquine in particular, have previously been shown to impair the immune response to intradermal (ID) rabies vaccination. A randomized controlled trial was performed in veterinary students to evaluate the antibody response to ID HDCV pre-exposure prophylaxis administered with and without chloroquine (3). The study consisted of 51 students not previously vaccinated against rabies, of which 26 received 300mg chloroquine base per week and 25 did not. All received 0.1 mL of rabies vaccine ID on days 0, 7, and 28. Chloroquine was given weekly to the treatment group starting 9 days before the first dose of vaccine and continued until day 48. Rabies-neutralizing antibody titers for the chloroquine group were significantly lower than for the control group on days 28, 49, and 105 post-vaccination, indicating that chloroquine taken in pre-exposure prophylaxis doses reduces the antibody response to primary immunization with ID HDCV. This observation was also reflected in a Peace Corp population in Thailand who had received chloroquine and had reduced immune responses to rabies vaccine (4). As a result, current ACIP guidelines recommend that exposed persons who are taking malaria prophylaxis should receive a fifth dose of rabies vaccine 28 days after the exposure. These guidelines do not differentiate between drugs used for malaria prophylaxis (5).

Obtaining rabies vaccine and rabies immune globulin in a deployed setting can be challenging (6). A full understanding of the requirements for protecting exposed individuals is necessary for appropriate decision making in a resource-constrained environment.

#### 2.2 Rationale

This is an exploratory trial to evaluate the effect of antimalarial drugs on the immune response generated by rabies vaccine when administered for post-exposure prophylaxis. This study will use the FDA approved post-exposure prophylaxis vaccine regimen (without rabies immune globulin) in the presence or absence of an FDA-approved malaria chemoprophylaxis regimen.

•

Rabies post-exposure prophylaxis in unvaccinated individuals who are not on malaria prophylaxis consists of four, 1.0-mL IM injections of the human diploid cell vaccine (HDCV) or purified chick embryo cell (PCECV) rabies vaccine on days 0, 3, 7, and 14 (5). In the event of an exposure, human rabies immunoglobulin (HRIG) would also be administered on day 0, at 20 units per kg of body weight, IM, preferably at the site of exposure and not in the same location as the first vaccine dose. In previously vaccinated individuals, HRIG is not administered, and two doses of vaccine are given, one at day 0 and one at day 3. Current ACIP guidelines recommend that because "corticosteroids, other immunosuppressive agents, antimalarials, and immunosuppressive illnesses might reduce immune responses to rabies vaccines substantially," exposed persons on antimalarials should receive a fifth dose of rabies vaccine on day 28. The guidelines do not differentiate between malaria prophylaxis regimens (5), therefore this fifth dose is indicated in all compliant soldiers serving in malaria-endemic areas.

This study will administer the post-exposure regimen to volunteers from a US population of military age who are taking one of three malaria prophylaxis regimens or no malaria prophylaxis. The primary endpoint is the rabies titer 28 days after the first dose or 14 days after completion of the 4-dose regimen given to individuals not on malaria prophylaxis (ie, the time point at which the fifth dose would be given) to determine if there is any added value in administering this fifth dose.

Malarone and doxycycline were chosen because they are the drugs most commonly prescribed to deploying soldiers for malaria prophylaxis. Chloroquine was chosen because this was the drug previously shown to affect the immune response to intradermal rabies vaccination given for pre-exposure prophylaxis (3). Its effect on the immune response to intramuscular rabies vaccines given in the regimen for post-exposure prophylaxis has not previously been studied.

#### 2.3 Potential Risks and Benefits

#### 2.3.1 Potential Risks

#### Subjects receiving Rabies Vaccine

Reactions to the current rabies vaccine are mild with local pain, erythema and swelling at the injection site. Systemic reactions are less frequent and include headache and malaise (1). Guillain-Barré syndrome has been reported as a rare event following vaccination but its association with vaccination is uncertain (1).

# Subjects receiving Chloroquine

Reactions to chloroquine include gastrointestinal upset, headache and pruritus, which may be intolerable, is common among Africans.

•

#### Subjects receiving Malarone

Reactions to malarone are nausea, vomiting, abdominal pain, headache, diarrhea, weakness, loss of appetite, and dizziness.

#### Subjects receiving Doxycycline

Reactions to doxycycline are mild nausea, mild diarrhea, gastrointestinal upset, mild skin rash, photosensitivity and itching and for females, vaginal itching or discharge. This medication may also have more severe symptoms such as headaches, fever, chills, severe diarrhea, and decreased urination.

#### All subjects

Potential risks of blood sampling include tenderness or bruising at the spot where blood was drawn. Fainting or dizziness can occur after a blood draw, but this is uncommon.

#### 2.3.2 Potential Benefits

Potential benefits to subjects receiving the rabies vaccine include potentially developing protective antibody levels to rabies.

There are no potential benefits to malaria chemoprophylaxis for this study.

#### **3 OBJECTIVES AND ENDPOINTS**

## 3.1 Study Objectives

#### 3.1.1 Primary Study Objective

To compare Geometric Mean Titer (GMT) at 14 days post completion of four dose post exposure prophylaxis (PEP) with PCECV in each of the malaria prophylaxis groups with control to determine if a fifth dose of PEP at that point would be of any added value.

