# 3.2 Study Endpoints

# 3.2.1 Primary Endpoint (Immunogenicity)

GMT by RFFIT at 14 days post completion of four doses PEP in prophylaxis groups vs. control group.

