#### 6.5 Preparation and Administration of Product(s)

RabAvert® rabies vaccine is reconstituted with 1 mL Water for Injection (WFI) and 1 mL is administered by IM injection in the deltoid muscle by CRU nurses. All subjects will receive four vaccinations. Schedule will be determined by group assignment.

Chloroquine, Malarone and Doxycycline are oral administration tablets.

The dose for chloroquine will be 500 mg po for once weekly administration for 6 weeks.

The dose for malarone will be 250/100 mg po once daily administration for 42 days.

The dose for doxycycline will be 100 mg po for once daily administration for 42 days.

See *Appendix A* and *Appendix B* for Study Events and *Appendix C* for Blood Draw Schedule.

MALRAB Version 11.0 09 May 2018

\_\_\_\_\_

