#### 12 STATISTICAL CONSIDERATIONS

# 12.1 Study Hypotheses

This will be a descriptive study to assess immunogenicity of a licensed rabies vaccine using test dosage schedules in the presence of malaria chemoprophylaxis. No formal statistical hypothesis tests will be conducted. Descriptive analyses will be based on the per-protocol analysis sets.

Exploratory statistical analyses of final data may be conducted, if indicated by the descriptive results. Parametric, non-parametric and resampling (bootstrapping) methods for statistical inference may be used in exploratory analyses, based on data compliance with assumptions of methods. P -values  $\leq 0.05$  will be considered significant and p-values  $\leq 0.10$  will be considered a trend. Confidence intervals will be constructed at  $\alpha$ =0.05 and  $\alpha$ =0.10. When necessary, p-value corrections for multiple comparisons will be applied.

Descriptive and any inferential analyses will be carried out using SAS Version 9.2 (or higher), which is licensed and supplied by SAS Institute, Cary, NC, USA.

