#### 12.2 Sample Size Considerations

The planned sample size is 100 subjects, who will be randomly allocated (1:1:1:1) into three treatment groups and one control group. The sample size was chosen empirically, based on sample sizes of other exploratory studies of this general type. This exploratory study is not powered to formally test equivalency or non-inferiority in immunogenicity among groups according to malaria prophylaxis. Subjects who withdraw prior to first vaccination will be replaced by the next enrolled subject who will be assigned to the same group as the withdrawn subject. Replacement subjects will not be randomized.

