Potential outliers will be identified using histograms and modified box plots or normal probability plots, when appropriate. Choice of subsequent tests for outliers (e.g. Grubbs, Tietjen-Moore and ESD) will depend on the number and nature of suspected outliers and may require data transformation. Bootstrapped estimates of standard errors may also be reported. Sensitivity analysis of effect of outliers on descriptive statistics will be conducted, and if necessary descriptive statistics that include and exclude outliers will be reported

Statistical Methods for Baseline Comparisons

Mean (SD) and median (IQR) age at baseline will be computed and descriptively compared across the six groups. Results will be presented in tabular format. Baseline mean (SD) and median (IQR) of all other quantitative demographic variables of interest at baseline will be calculated for each group and the results will be presented in a table.

The number and percentage of males and females per group at baseline will be calculated and results will be presented in tabular format. The number and percentage per group at baseline of all other qualitative demographic variables of interest will be calculated for each group and the results will be presented in tabular format.

Statistical Methods for Subject Disposition

For each group (three prophylaxis and one control), the number and percentage of subjects who received a total of 0, 1, 2, 3 and 4 rabies vaccinations will be reported in tabular format.

For each group, a line listing of subjects who discontinued the study that includes classification of the most serious reason for termination will be produced.

Statistical Methods for Primary Immunogenicity Objectives

Primary Objective: Compare GMT at 14 days post completion of four dose PEP with PCECV in each of the malaria prophylaxis groups with control to determine if a fifth dose of PEP at that point would be of any added value.

Immunogenicity against rabies will be assessed descriptively using the following parameters:

Timepoints: At 14 days post-completion of four doses of rabies vaccine

 Geometric mean titer (GMT) against rabies virus for the prophylaxis and control groups at 14 days after completion of four doses of vaccine.

A table that presents the total number of per-protocol subjects and GMT against rabies at 14 days post completion of four doses of vaccine by group will be produced.

Statistical Methods for Secondary Immunogenicity Objectives

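### The primary objective promises to determine whether a fifth dose adds value, but similar GMTs after four doses could not support a conclusion that it does not

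*Protocol*

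**What the plan says.** Protocol Section 3.1.1 sets the primary objective as comparing GMT in each malaria prophylaxis group with control, 14 days after the four-dose course, "to determine if a fifth dose of PEP at that point would be of any added value". The synopsis and the SAP (Statistical Methods for Primary Immunogenicity Objectives) carry the same clause. Section 2.2 gives the purpose of the primary endpoint as "to determine if there is any added value in administering this fifth dose", and explains that the sample falls when the fifth dose would be given. The endpoint in Section 3.2.1 is "GMT by RFFIT at 14 days post completion of four doses PEP in prophylaxis groups vs. control group".

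On design, Section 6.5 states "All subjects will receive four vaccinations", in line with Table 1 in Section 4.

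On inference, Section 12.1 states "No formal statistical hypothesis tests will be conducted" (the SAP agrees), and Section 12.2 states "This exploratory study is not powered to formally test equivalency or non-inferiority in immunogenicity among groups according to malaria prophylaxis". P-values and confidence intervals appear only among exploratory analyses that may be done if the descriptive results suggest them. The SAP's primary output, split by study group, is "A table that presents the total number of per-protocol subjects and GMT against rabies at 14 days post completion of four doses of vaccine". Section 8.2.1 names 0.5 IU/mL as an adequate response, but no planned table reports the proportion reaching it at the primary time point. The comparison of GMT with a protective titer is a secondary objective at other time points (Section 3.1.2).

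**The concern.** The objective is worded as a determination, and the plan does not say which result would settle it. No margin is given, and no rule links a GMT or a GMT ratio to added value.

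The two possible results are not symmetric. A clearly lower GMT on a drug would support the premise that the drug weakens the response. A GMT close to control would support omitting the fifth dose only through a non-inferiority inference, which the protocol says it is not powered to test formally. The planned table does not even show how large a deficit remains compatible with the data.

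The stake is the direction of the likely error. Sections 2.1 and 2.2 set the study against a current recommendation of a fifth dose for people on antimalarials, and Section 2.1 cites decisions in resource-constrained settings. A descriptive finding of no visible difference, read through this objective, could be taken as evidence that the extra dose is unnecessary.

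**Working it through.** **The plan's own figure.** The planned size is 25 per group, 100 in total. It cannot be reproduced from a formula, because Section 12.2 says it was chosen empirically and gives no effect size, SD, margin or power. Only the allocation can be checked. By Section 5.4.1, 39 subjects at 1:1:1 and then 61 at 2:1:1:1 give 61 × 2/5 = 24.4 on chloroquine and 39/3 + 61/5 = 25.2 in each other group, consistent with 25.

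**Inputs.** n = 25 per group (Table 1); 95% intervals (Section 12.1, α = 0.05); threshold 0.5 IU/mL (Section 8.2.1). The SD of log10 titer is not given, so 0.3 to 0.6 is assumed.

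**What an observed ratio of exactly 1 would leave open.** SE = SD × √(2/25). The 95% CI is the ratio multiplied and divided by 10^(t × SE), with t(0.975, 48 df) = 2.011.

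| Assumed log10 SD | SE | CI factor | Lower limit | Deficit not excluded |
|---|---|---|---|---|
| 0.3 | 0.085 | 1.48 | 0.68 | 32% |
| 0.4 | 0.113 | 1.69 | 0.59 | 41% |
| 0.5 | 0.141 | 1.92 | 0.52 | 48% |
| 0.6 | 0.170 | 2.19 | 0.46 | 54% |

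Per-protocol exclusions widen this. With an assumed 20 evaluable per group, the factors are 1.56, 1.80, 2.09 and 2.42.

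**Proportion at or above 0.5 IU/mL.** If all 25 reach it, the exact two-sided 95% lower bound is 0.025^(1/25) = 0.863, so up to 13.7% below is not excluded. With 24 of 25 the bound is 79.6%, leaving 20.4%. With 20 of 20 it is 83.2%.

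**The indirect route as a formal test.** Normal-approximation power for non-inferiority at one-sided 0.025 with true ratio 1 is Φ(log10(margin)/SE − 1.96). Both margins are illustrative, since the documents give none.

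| Assumed log10 SD | Power, two-fold margin | Power, 1.5-fold margin |
|---|---|---|
| 0.3 | 94% | 55% |
| 0.4 | 76% | 34% |
| 0.5 | 57% | 24% |
| 0.6 | 43% | 18% |

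**The opposite direction.** The fold difference detectable with 80% power at two-sided 0.05 is 10^((1.960 + 0.842) × SE), which runs from 1.73 (SD 0.3) to 2.99 (SD 0.6). A large deficit is therefore within reach of 25 per group.

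**The case against.** A reader might infer that, because nobody receives a fifth dose, the design is faulty or the question cannot be studied at all. The documents do not support this. Section 2.2 says the fifth dose is recommended because antimalarials might reduce the response. The study looks at that premise directly, with and without drug, when the dose would be given. The missing arm rules out estimating the increment from a fifth dose. It does not rule out describing whether the reason for one is present.

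A reader might also infer that the objective yields nothing. That goes too far. The study of intradermal vaccine described in Section 2.1 found significantly lower titers with 26 students on chloroquine and 25 not. A deficit of that kind could be described here and would be informative.

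The strongest defence is disclosure. The protocol calls itself exploratory and descriptive and disclaims power for formal equivalence or non-inferiority tests. It nowhere says that a null result will be reported as no added value. The size of the problem also depends on an SD that the documents do not give: at 0.3, power for a two-fold margin would be 94%.

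All of this stands, and it narrows the point to one direction of inference. It does not remove it. The disclaimers sit in Section 12, while the objective, in four places, still says that the comparison will determine the matter. The favourable power figure needs a margin that the plan does not set.

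**Conclusion.** The point holds in one direction. Followed as written, the plan could describe a clear deficit on a drug, but similar GMTs could not support a conclusion that a fifth dose has no added value.

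With equal observed GMTs and 25 per group, deficits of about 32% to 54% stay within the 95% interval. This rests on the assumed SD range, full evaluability and an observed ratio of exactly 1. The bound of 13.7% below 0.5 IU/mL needs no SD but supposes 25 of 25 responders. No control titer is given, so the documents do not show whether a fall of this size would bring subjects near the threshold.

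The fault lies in the wording of the objective and in a primary table too thin to show the uncertainty. The absence of a fifth-dose arm is not itself an error, and nothing here bears on which vaccination schedule is right.

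**What to change.** 1. In the synopsis, Sections 2.2 and 3.1.1, and the SAP primary objective, replace the purpose clause. The aim becomes to estimate the difference in GMT between each prophylaxis group and control at the time a fifth dose would be given.
2. In the SAP primary analysis, add the GMT ratio of each drug group to control with a 95% CI. As a supportive descriptive summary, not a new primary outcome, add the proportion at or above 0.5 IU/mL in each group with an exact 95% CI.
3. State in the protocol and SAP that similar GMTs, or a non-significant difference, will not be reported as showing that a fifth dose has no added value.

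No new arm, subjects or samples are needed. The RFFIT result at this time point is already planned, and Section 12.3 and the SAP already have rules for values below LLOQ in titer ratios. The costs are a less ambitious claim, a little extra tabulation, and a wording amendment that needs IRB approval (Section 15.2). The amendment would come late: the protocol is Version 11.0 of 9 May 2018, and the synopsis lists a period ending in August 2018. This is a reason to date the change clearly and to keep the proportion supportive.
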